8.0 Data Safety and Monitoring Plan

A clinician advisory panel comprising 9 speech-language pathologists who work in critical care has been established to guide this study. Additionally, 3 physicians have agreed to provide medical advice to the study team. The clinician advisory group will meet via video-conference every 4-6 weeks over the course of the study. [name], PhD, SLP(C), Reg. CASLPO will act as chair. Progress reports will be provided for review 1 week ahead of these meetings, and presented to the meeting. These reports will document the numbers of participants accrued, preliminary trends in the data and any adverse events. After discussion, the principal investigator, co-investigators, collaborators and study coordinators will leave the call, to allow for further in camera discussion. In the event that any concerns about study continuation are raised during the in camera session, [name] will report these back to the study team.

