5.0 Selection of Subjects

Participants

We aim to conduct 100 assessments (approx. 25 per collaborating site involved in the study and approx. 50 at University Health Network) over a 14-month period.

Recruitment

We will adopt three strategies for recruiting participants to this study:

1) We have linked to the Ontario COVID-19 Prospective Cohort Study (OnCoP) study being conducted by the CANCOV study PIs Drs. [name] and [name] at UHN. The CANCOV study team has agreed to notify their participants of the opportunity to participate in our study. They will use our

study information sheet and referral form for this purpose. They have also suggested that a Swallowing Team Member could attend their weekly clinic and speak directly to CANCOV participants who agree to consider the study.

2) We will work through the members of our clinician advisory group and a wider network of clinicians in the cities where data collection is happening to solicit referrals of patients who meet the study inclusion criteria. We will ask these clinicians to introduce the study opportunity to patients and request permission to complete a referral to the study team for future contact.

3) We will conduct a broad public advertising campaign through local newspapers, magazines, websites, mailings and posters at community centres, seniors' residences, places of worship, and around the university and hospital campuses of the study sites (University of Toronto, University Health Network Toronto, McMaster University, Hamilton Health Sciences Centre, University of Florida, Shands Medical Centre).

The clinical research coordinator will respond to all inquiries or referrals regarding potential participation, contacting the patient by phone or videoconference using Microsoft Teams to discuss the study further, obtain initial verbal consent and schedule the study appointments. A reminder call will take place 2 days before the scheduled study appointments.

Inclusion Criteria

- Adult (18 years of age or older)
- Positive (or presumed positive) diagnosis of COVID-19 infection not earlier than March 1, 2020
- At least 2 weeks post positive diagnosis and medical management of COVID-19 infection

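### Clinicians on the advisory panel who may refer participants also receive interim data trends every 4 to 6 weeks, which leaves a small, avoidable route to selective referral

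*Combined protocol and SAP*

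**What the plan says.** Section 8.0 (Data Safety and Monitoring Plan) describes the panel: "A clinician advisory panel comprising 9 speech-language pathologists who work in critical care has been established to guide this study". On timing it says: "The clinician advisory group will meet via video-conference every 4-6 weeks over the course of the study". A progress report is circulated a week before each meeting and then presented. On content: "These reports will document the numbers of participants accrued, preliminary trends in the data and any adverse events". Afterwards "the principal investigator, co-investigators, collaborators and study coordinators will leave the call, to allow for further in camera discussion", and any concern about continuing the study is reported back to the study team. Three physicians are also available to give the team medical advice.

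Section 5.0 (Recruitment, second strategy) names the same group as a source of participants: "We will work through the members of our clinician advisory group and a wider network of clinicians". Their task is then set out: "We will ask these clinicians to introduce the study opportunity to patients and request permission to complete a referral to the study team". The other two strategies are a link to an existing COVID-19 cohort study and public advertising.

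Section 7.0 gives the aim as the prevalence of abnormal values, compared with reference data that have already been collected.

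**The concern.** Some of the people who decide which recovering patients to approach are shown, at regular intervals, how the results are developing. Accrual and adverse events are listed separately in the report, so the natural reading of the remaining item is swallowing findings. A clinician who hears that abnormal swallows are common, or commoner in some kind of patient, may refer more or fewer such patients afterwards, without intending to.

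The main result is a frequency in whoever is enrolled, so a change in case mix moves it directly. Nothing in Section 5 asks for consecutive referral or a log of patients considered. Section 7 says the data will not support a multivariate model of the moderators, so a drift could be described but hardly adjusted away. The trends also serve no stated purpose: the plan names no decision that uses them.

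**Working it through.** The plan gives no figure for this point, so there is none to reproduce. The check is a cross-reading, a count of reports and an illustration of size.

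**Cross-reading**

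| Question | Section 5.0 | Section 8.0 |
|---|---|---|
| Who? | Advisory group members, plus a wider clinician network | The advisory panel |
| What do they do? | Introduce the study and seek permission to refer | Read and hear interim trends, then confer in camera |
| What separates the roles? | Nothing stated | The study team leaves the call; members who refer are not asked to |

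**Number of reports**

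The Protocol Summary gives accrual from 15 October 2020 to 31 January 2022, which is 365 + 108 = 473 days.
- At 6-week intervals: 473 / 42 = 11.3
- At 4-week intervals: 473 / 28 = 16.9

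That is about 11 to 16 complete reporting cycles. The 14-month period in Section 5 (about 426 days) gives 10.1 to 15.2.

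**Illustration of size**

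None of these inputs is in the documents; all are assumptions.
- Unsafe swallows occur on 20% of boluses in a high-risk subgroup and on 5% in other participants.
- The high-risk share is 30% without any influence from the reports.
- A fraction *s* of participants comes through panel members, and the high-risk share among them rises to 50%.

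Frequency at a 30% share: 0.30 × 20% + 0.70 × 5% = 9.5%.
Frequency at a 50% share: 0.50 × 20% + 0.50 × 5% = 12.5%.
Pooled frequency: (1 − *s*) × 9.5% + *s* × 12.5%.

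For *s* = 1/3: (2/3) × 9.5% + (1/3) × 12.5% = 10.5%.
Odds ratio against 9.5%: (0.105 / 0.895) / (0.095 / 0.905) = 0.1173 / 0.1050 = 1.12.

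| Assumed fraction whose mix shifts | Pooled frequency | Odds ratio against 9.5% |
|---|---|---|
| 1/6 (later half of one third) | 10.0% | 1.06 |
| 1/4 | 10.25% | 1.09 |
| 1/3 | 10.5% | 1.12 |
| 1/2 | 11.0% | 1.18 |
| All participants | 12.5% | 1.36 |

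The last row is only an upper limit under these assumptions, because the panel is not the sole source of participants. If it supplied one third, a pooled 12.5% would require its own high-risk share to reach 90%: 9.5% + (1/3) × 15% × (0.90 − 0.30) = 12.5%.

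**Would safety counts be neutral?**

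Under Section 4.0 (Stopping rules), testing stops early because of aspiration or serious residue. The primary outcomes in Section 3.2 are unsafe swallows on the Penetration-Aspiration Scale and pharyngeal residue. Counts of stopping events would therefore give referrers a close proxy for both primary outcomes.

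**The case against.** The strongest reply is that little added bias is shown. The cohort is already a convenience sample. The protocol openly predicts abnormal swallowing, and these clinicians are specialists who expect it. The panel is part of one of three routes, and ventilator history and dyspnea are recorded, so case mix can be described. All of this stands, and it is why the point is minor. It does not supply a reason to send the trends.

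Several stronger readings are tempting, and the documents do not support them.

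- A reader might infer that referrers learn which patients, or which kinds of patient, have abnormal swallows. Section 8 mentions no breakdown, and Section 9.0 restricts participant information and raw data to named study personnel.
- A reader might set an odds ratio near 1.36 against the design target of 2.00. That figure needs the whole cohort to shift. It also compares two case mixes of patients, whereas the target compares patients with a healthy reference.
- A reader might blame the lack of a concurrent control group. A concurrent healthy group would not absorb a drift in severity among patients.
- A reader might conclude that members must choose between referring and joining the in camera session. The panel is advisory, has no stated power to stop the study and reports concerns back. The study team leaves for that session, and physicians advise separately. For a two-visit observational study, stricter separation is a governance preference; the documents do not require it.
- A reader might object that the investigators hear the trends too. Section 4.0 (File Transfer) places all data processing in the Toronto laboratory, so withholding them from the meeting would change little for that team.

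**Conclusion.** The overlap is plain from Sections 5 and 8: members of one advisory group may refer participants and also receive interim data trends, about 11 to 16 times over accrual. It opens a possible route to selection bias in the frequency of abnormal swallows; it does not show that bias will occur. The size cannot be derived from the documents, because neither the split of participants by route nor the detail of the reports is given. With an assumed fraction of one quarter to one half of participants affected, the odds ratio from referral mix alone is about 1.09 to 1.18, with 1.12 at one third. The conclusion also rests on reading the trends as swallowing findings, which is the natural reading but is not spelled out. Minor in severity, and worth closing because closing it costs almost nothing.

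**What to change.** 1. In Section 8, remove the item on data trends from the reports and presentations to advisory members while enrolment is open. Limit these to accrual and adverse events.
2. State that counts of stopping events for aspiration or residue are withheld from members who refer. They can go to non-referring members or to the medical advisers, so that safety review is kept. The protocol does not say whether aspiration seen on videofluoroscopy counts as an adverse event; if it does, handle those counts in the same way.
3. In Sections 5 and 7, record each participant's referral source and enrolment date, and describe the primary frequencies by recruitment route and over calendar time. This would make any drift visible.

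The cost is a reworded paragraph, a revised report template and two data fields. The one downside is that advisory clinicians lose an early view of findings on which no stated decision depends. All three recruitment routes remain open.

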9.0 Data Handling and Record Keeping

Routine practices for ensuring the confidentiality and privacy of all participants will be followed in this study. All research personnel at the Toronto Rehabilitation Institute are required to sign a confidentiality agreement at the time of hire. Research personnel at McMaster University and the University of Florida are similarly bound by a confidentiality agreement outlined by the ethics board at their institutions.

Participants will be assigned a non-identifying alphanumeric study code, and the master key for this code will be retained separately by the lead investigators at each site ([name], [name], [name]) on a secure, password-protected, encrypted research server. Paper-based

[name]. The Pathophysiology of Swallowing Impairment in People Recovering from COVID-19 Infection.

documents will be stored securely in a locked filing cabinet under the supervision of the lead investigators at each site.

De-identified hard copy data will be transcribed onto an electronic file and transferred to [name] lab at the KITE Research Institute – Toronto Rehabilitation Institute - University Health Network. Routine daily back-up of this research server will be performed to protect against data loss.

All de-identified data will be transferred to [name] using an encrypted file transfer portal, for subsequent analysis. Only the participant's alphanumeric study code number will appear on the data collection sheets and in the data collection files.

Access to participant information and experimental raw data will be restricted to the study personnel named in this application. All records will be destroyed after 10 years under the supervision of [name], [name] and [name].

In the event of inappropriate release of personal health information, further release of information will be stopped, any information that can be retrieved will be retrieved, the UHN Privacy Office and REB will be notified. If applicable, the REB at McMaster University and the University of Florida IRB will be notified. Any recommended further actions will be taken.

10.0 Conflicts of interest

[name], the principal investigator, holds current and prior research contracts with Bracco Canada and Nestlé Health Science, who are manufacturers of the barium products and thickening agents that will be used in this study. She has also served in an advisory capacity on expert panels for Nestlé Health Science. These relationships will be disclosed to participants in the study information sheet. All products for use in the study will be purchased. Neither Bracco Canada nor Nestlé Health Science will have any role as sponsors of this study. [name] will not receive any financial payment, either personally or to the lab, related to the use of Nestlé or Bracco products in this study.

11.0 Additional Ethics Reviews

Additional ethics approvals have been separately obtained for other sites involved in this study as follows:

- University of Florida
- McMaster University

